4.4 END OF STUDY DEFINITION

The study intervention will be up to 10 days in length. Vagus stimulation will be performed 4 times daily (approximately at 6:30AM, 11:30AM, 4:30PM and 9:30PM). Data collection will continue till hospital discharge. If the participant becomes hemodynamically unstable, defined as hypotension requiring vasopressors the VNS will be held for safety purposes. However, it will be resumed, once the patient is stabilized, off vasopressors for 48 hours. If the patient is being hemodynamically augmented for symptomatic vasospasm, n-VNS will not be withheld as the beneficial effects of n-VNS on symptomatic vasospasm will be investigated in this study.

Participants must fulfill all of the inclusion criteria in order to be eligible for the study:

- Established signed and dated informed consent form
- Can be enrolled within 5 days of cerebral aneurysm treatment.
- CT of the head revealing blood in the subarachnoid space
- Subject has ruptured cerebral aneurysm or SAH patients who do not have vascular malformation on cerebral angiogram.
- Subject is male or female 18 -75 years of age
- Subject is alert able to verbalize pain at the time of enrollment
- Subject reports pain of 7 and greater on a 10 Point Pain numeric rating scale or presenting with severe headache.
- Female of reproductive age must have a negative pregnancy test (Urine or blood test)

nVNS will only be performed if vital signs are stable (HR>60, SBP> 100 mmHg, MAP> 60 mmhg, and saturation > 90% on room, nasal cannula or face mask). Then the vagus nerve will be stimulated.

5.2 EXCLUSION CRITERIA

Patient who meets any of the following criteria will be excluded:

- Use of any concomitant electrostimulation devices (Pacemaker, defibrillator, deep brain stimulation.)
- Unsecured ruptured aneurysm defined as aneurysm that has not been surgically or endovascularly treated. Previous carotid surgeries or known history of carotid artery disease
- Screws, metals or device in the neck
- History of secondary or tertiary heart blocks, ventricular tachycardia, SVT (including atrial fibrillation)
- Alcoholics (CAGE scale of 2 or greater). If patients are on CIWA protocol for alcohol withdrawal, the patient will be excluded from the study.
- Drug addicts or chronic opioid users confirmed by history or with urine toxicology showing opiates or cocaine
- Traumatic subarachnoid hemorrhage
- Thin cortical subarachnoid hemorrhage not due to a cerebral aneurysm

Fria

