A recent systematic review of 51 studies evaluating the safety of noninvasive VNS, revealed that it is safe and well tolerated with minimal side effects. Skin irritation was the most common side effect, followed by headache accounting for 3.6% and nasopharyngitis in 1.7%. (20) Cardiac side effects are one of the most feared complications of invasive VNS. However, the review, which included patients with previous cardiac disease, found that cardiac side effects from nVNS on either side are minimal, accounting for only 1 out of the 1322 patients. The individual developed symptomatic bradycardia after nVNS.(20) In addition, there are ongoing studies evaluating the usefulness of nVNS in heart failure. Other rare complications are dizziness, facial palsy, nausea and vomiting. In addition, Redgrave et al could not show that side effects correlated with nVNS dose.(20) nVNS has not been studied in patients with subarachnoid hemorrhage or brain aneurysms, however the invasive form has been used in patients with cerebral vascular malformations, and we are unaware of any cases in the literature of intracranial hemorrhage due to VNS. There is an ongoing clinical trial on safety of noninvasive VNS, in moderate traumatic brain injury which include "operative intracranial lesions". (21) A recent pilot study with invasive VNS in chronic stroke showed that it was feasable, tolerable and safe.(22) Given the lack of human studies in aneurysmal SAH, only patients with completely treated aneurysms will be part of the study. It is important to include this patient population given the potential benefits of VNS in controlling secondary brain injury (strokes and delayed cerebral ischmia) thought to be due to inflammation and cortical spreading depression. These secondary complications seen in a-SAH are not typically seen in other causes of SAH. In addition, a recent study on nVNS in a mouse model with cerebral aneurysm ahowed that daily stimulation of the vagus nerve could be actually protective and decreased the risk of aneurysmal rupture(13). Other vascular malformations will be excluded, given that their interventional treatment is more complicated. It is unknown if nVNS has long-term side effects, however, studies have shown that most common long-term complications seen in the invasive

form were due to recurrent surgeries for device malfunction (battery and lead replacement). This is bypassed with the nVNS.

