2.3.3 ASSESSMENT OF POTENTIAL RISKS AND BENEFITS

Although the risks of nVNS in SAH population are unknown, a recent study in a mouse model of SAH showed that it decreased aneurysmal rupture rate and improved outcomes in those with ruptured aneurysm. The authors noted the potential for nVNS in humans and the ability to translate their research to human studies.(13) To minimize risks, if an aneurysm has been identified to be the cause of the SAH, patients will only be enrolled when the aneurysm has been completely treated. In addition, while in the NSCU, patients will be continuously monitored via telemetry, with frequent BP measurement. Studies conducted on patients with migraine and cluster headache were conducted as outpatient. Our patients are continuously monitored, and the medical staff are well equipped to treat any medical emergency. Vagus nerve stimulation will only be administered if the vital signs are stable (SBP>100 mmHg, MAP>60 mmHg, HR>60, Oxygen saturation > 90%).

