5.4 PRE-SCREEN FAILURES

Individuals who do not meet the criteria for participation in this trial (pre-screen failure) because of unsecured aneurysm intubated or has symptomatic hydrocephalus or symptomatic bradycardia may be rescreened once the aneurysm is secured, patient is extubated and stabilized, and EVD is placed. Rescreened participants should be assigned the same participant number as for the initial screening.

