5.5 STRATEGIES FOR RECRUITMENT AND RETENTION

The neurosurgical critical care unit (NSCU) at Northshore University Hospital is the main referral unit for the healthcare system for patients with subarachnoid hemorrhage. All transferred patients

are admitted to the NSCU, as a result, patients can be easily identified by the research team on a daily basis. Every day, the neurointensivist or the research coordinator will evaluate which patients admitted to the NSCU have been diagnosed with subarachnoid hemorrhage. If an aneurysm is found to be the cause of the SAH, surgical or endovascular treatment of the aneurysm is typically performed within 72 hours of diagnosis. Patients will be included in the study once the aneurysm has been treated. The primary investigator, or sub investigators will take consent from the patient. The primary investigator will ensure that the sub investigators and research assistants are trained and knowledgeable of the research protocol. Patients enrolled in the study will be followed up to 10 days starting 24 hours post successful treatment of the aneurysm unless discharged earlier from the hospital.

We admit on average 110 SAH cases a year. If we assume that 50% satisfy our inclusion criteria, and that 70% will sign the inform consent, we should be able to reach our target number in approximately 12 months. Patients identified in the NSCU will be approached by the research team, and the study will be explained to them.

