8.2 SAFETY AND OTHER ASSESSMENTS

nVNS has been proven to be safe. However, the risks of VNS in SAH population are not known. In order to minimize the risks, if an aneurysm has been identified to be the cause of the SAH, patients will only be enrolled if the aneurysm has been completely treated. This information will be pulled from the medical record. Past medical and surgical history, respiratory and hemodynamic state will be pulled from the medical record. Vital signs and neurologic examinations are usually performed every 1 to 4 hours depending on the acuity of each case, and pain assessment evaluated every 4 hours and as needed. In the NSCU, patients are on continuous ECG analyzes via telemetry. Stimulation will only be given if HR >60 and the SBP>100 mmHg, MAP> 60 mmHg and oxygen saturation is >90% for safety concerns. The presence of intolerable pain at the stimulation site, skin irritation, hoarseness, and change in the taste, shortness of breath, chest pain, nausea, and vomiting will be evaluated.

Safety outcomes:

- Rate of Symptomatic bradycardia defined as a drop in HR to less than 60 beats per minutes with symptoms, not due to nimodipine. The timing of nimodipine relative to the VNS will be recorded. All patients are on telemetry during the stimulation.
- Rate of drop in blood pressure, defined as a drop in blood pressure requiring fluid resuscitation or vasopressor support thought to be due to the device.
- Rate of side effects: presence of intolerable pain at the stimulation site, skin irritation, nasopharyngitis, hoarseness, dysgeusia, shortness of breath, chest pain, nausea and vomiting.

Figure

Days 1-3	Screening			
 Total n=40 Obtain informed consent Screen potential participants by inclusion and exclusion criteria Obtain history, document Randomize 				
Days 2-4 till discha from ICU	rge Baseline assessments/ Study Intervention			
 Obtain daily cumul Evaluate presence Evaluate seizures d Complete vital sign Questionaire for sign 	as before and after each stimulation and daily trend de effects from VNS post every stimulation scranial dopplers (TCD) comatic vasospaspm I fever			
Discharge from the hospital or day 10 post-ictus				

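### The protocol says only patients with a completely treated aneurysm are enrolled, but the listed eligibility criteria do not carry that condition

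*Protocol*

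**What the plan says.** Three places in the protocol state a strict condition. Section 2.3.1, after noting the absence of human studies in aneurysmal SAH, says "only patients with completely treated aneurysms will be part of the study". Section 2.3.3 introduces its version as a step to reduce risk: "patients will only be enrolled when the aneurysm has been completely treated". Section 8.2 repeats it for the same reason: "patients will only be enrolled if the aneurysm has been completely treated". Section 8.2 adds that the information comes from the medical record.

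The text that decides eligibility is worded differently. The section 5.2 exclusion is "Unsecured ruptured aneurysm defined as aneurysm that has not been surgically or endovascularly treated". The inclusion list, printed after section 4.4, has two entries that touch the aneurysm. One is about timing, "Can be enrolled within 5 days of cerebral aneurysm treatment", and one is about cause, "Subject has ruptured cerebral aneurysm or SAH patients who do not have vascular malformation on cerebral angiogram". Section 5.4 lets a pre-screen failure return: such a patient "may be rescreened once the aneurysm is secured", subject to other clinical conditions. Section 5.5 says "Patients will be included in the study once the aneurysm has been treated".

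A further term, successful treatment, appears in the synopsis (section 1.1) and in section 5.5, where it fixes the start of the study period. The SAP contains no eligibility criteria.

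**The concern.** Section 2.3.1 says the device has not been studied in patients with SAH or brain aneurysms, and section 2.3.3 says its risks in SAH are unknown. Complete treatment of the aneurysm is one of the measures offered in response, alongside telemetry, frequent blood pressure measurement and the vital-sign conditions for stimulation. A safeguard of that kind should stand in the criteria against which each patient is checked. Here it stands only outside them.

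Two things are at stake. The first is participant safety: someone whom the risk assessment treats as outside the study could be cleared by a checklist built from the inclusion and exclusion lists. The second is the description of the population. The primary safety endpoint is the incidence of device-related serious adverse events. A reader of that result needs to know which aneurysm status the participants had, and the documents currently support more than one answer.

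**Working it through.** No arithmetic applies and the plan gives no figure to reproduce. The check is to take one test patient through every provision on aneurysm status.

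Test patient: a ruptured aneurysm; a surgical or endovascular procedure within the enrolment window; treatment not complete; every other criterion met.

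| Provision (protocol) | What it asks about the aneurysm | Result for the test patient |
|---|---|---|
| Inclusion list, timing | Enrolment within five days of treatment | Passes |
| Inclusion list, cause | Ruptured aneurysm, or SAH without a vascular malformation | Passes |
| Section 5.2, unsecured aneurysm | Has it been surgically or endovascularly treated? | It has, so not excluded |
| Section 5.2, remaining bullets | None concerns completeness of treatment | Not excluded |
| Section 5.4, re-screening | Is it secured? The only available definition is the reverse of section 5.2's | May be re-screened |
| Section 5.5, recruitment | Has it been treated? | May be included |
| Sections 1.1 and 5.5, study period | Was treatment successful? The term is undefined | Cannot be determined; sets the clock, not eligibility |
| Sections 2.3.1, 2.3.3 and 8.2 | Has it been completely treated? | Barred |

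The next question is which provisions control randomisation. Section 8.1 says that patients found to satisfy the inclusion and exclusion criteria, with consent signed, are randomised. It names the lists and does not refer to the condition in sections 2.3.1, 2.3.3 and 8.2.

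So the test patient passes the lists that section 8.1 relies on and fails the condition in three other sections. Neither *completely treated* nor *successful* is defined anywhere in the protocol or SAP, so the text offers no rule for resolving the difference.

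**The case against.** The strongest reply is that the protocol does contain the strict condition, and not only as background. Section 8.2 belongs to the chapter on study assessments and procedures, states the restriction on enrolment, and names the source for verifying it. The two rules are also compatible: section 5.2 removes untreated ruptured aneurysms, the other sections narrow enrolment further, and nothing says that a partly treated aneurysm may be enrolled. The study is described as single-site, and section 5.5 makes the primary investigator responsible for seeing that staff know the protocol.

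Much of this stands. A reader might infer that the protocol permits incompletely treated aneurysms, or that staff would enrol them. The documents do not support either reading. Staff who apply section 8.2 would turn the patient away. What remains is that the patient *could* be enrolled by someone working from the criteria, because the criteria lack the condition.

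The second reply is that treated, secured, successfully treated and completely treated are loose synonyms, and that the start of the study period 24 hours after successful treatment closes the gap in any case. This is weaker. Section 5.2 supplies its own definition of unsecured and leaves completeness out. *Successful* is undefined, is not a listed criterion, and is used only to start the clock. If the authors did mean the terms as equivalents, the text does not show it, and the remedy is the same.

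**Conclusion.** The point holds as an internal inconsistency: a stated safety condition on enrolment is missing from the listed criteria under which patients are randomised. This rests on the wording alone and needs no numerical assumption.

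Its size in patients cannot be given. A count among the 40 participants would need the share with an aneurysmal cause and the share of those incompletely treated. The documents give neither, and the inclusion list also admits SAH without a vascular malformation. It would also require that the condition in sections 2.3.1, 2.3.3 and 8.2 be overlooked each time.

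A reader might also infer that a rebleed in such a patient could not be told apart from device risk, or that the safety endpoint will come from a higher-risk population than the one described. The documents do not support going that far. There is a concurrent sham group under 1:1 allocation (section 6.3) and a graded relatedness assessment (section 8.3.2.2). Both will be imprecise with 40 patients, but that applies to every event. No shift in the population is shown either.

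The correction is worth making because it is cheap and concerns a protection the protocol itself relies on.

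**What to change.** Reconcile sections 2.3.1, 2.3.3, 5.2, 5.4, 5.5 and 8.2 and the inclusion list so that one defined aneurysm status governs enrolment, and use the same term throughout. Align the successful-treatment wording in sections 1.1 and 5.5 with it, or define it separately if it is meant only to start the study period. Which status applies is for the sponsor and clinicians to decide.

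Add one field to the eligibility case report form, completed before randomisation, recording that status and its source, with a not-applicable option for non-aneurysmal SAH. The source can be the medical record named in section 8.2 and the radiology from after the aneurysm is secured, which section 8.1 already lists for review at screening. The definition should also say which record counts when no post-procedure angiogram is available, since the documents do not show that every patient will have one.

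The cost is a wording amendment with IRB approval and one form field. If the stricter wording is kept, a few candidates may become ineligible.

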5.3 LIFESTYLE CONSIDERATIONS

There will be no lifestyle modification related to the study

5.4 PRE-SCREEN FAILURES

Individuals who do not meet the criteria for participation in this trial (pre-screen failure) because of unsecured aneurysm intubated or has symptomatic hydrocephalus or symptomatic bradycardia may be rescreened once the aneurysm is secured, patient is extubated and stabilized, and EVD is placed. Rescreened participants should be assigned the same participant number as for the initial screening.

5.5 STRATEGIES FOR RECRUITMENT AND RETENTION

The neurosurgical critical care unit (NSCU) at Northshore University Hospital is the main referral unit for the healthcare system for patients with subarachnoid hemorrhage. All transferred patients

are admitted to the NSCU, as a result, patients can be easily identified by the research team on a daily basis. Every day, the neurointensivist or the research coordinator will evaluate which patients admitted to the NSCU have been diagnosed with subarachnoid hemorrhage. If an aneurysm is found to be the cause of the SAH, surgical or endovascular treatment of the aneurysm is typically performed within 72 hours of diagnosis. Patients will be included in the study once the aneurysm has been treated. The primary investigator, or sub investigators will take consent from the patient. The primary investigator will ensure that the sub investigators and research assistants are trained and knowledgeable of the research protocol. Patients enrolled in the study will be followed up to 10 days starting 24 hours post successful treatment of the aneurysm unless discharged earlier from the hospital.

We admit on average 110 SAH cases a year. If we assume that 50% satisfy our inclusion criteria, and that 70% will sign the inform consent, we should be able to reach our target number in approximately 12 months. Patients identified in the NSCU will be approached by the research team, and the study will be explained to them.

6 STUDY INTERVENTION

6.1 STUDY INTERVENTION(S) ADMINISTRATION

GammaCore has received FDA approval/clearance for the treatment of acute migraine and acute or preventive treatment of cluster headache. It has not been studied for the treatment of headache in SAH. Given the shared pathogenesis of headache in SAH and migraine, we would like to test the device in SAH patient population. Per the GammaCore IFU: "gammaCore Sapphire[™] (non-invasive vagus nerve stimulator) is a multi-use, hand-held, rechargeable, portable device consisting of a rechargeable battery, signal-generating and -amplifying electronics, and a control button for the subject to adjust the signal amplitude. GammaCore Sapphire provides visible (display) and audible (beep) feedback on the device and stimulation status. A pair of stainless steel surfaces, which are the skin contact surfaces (stimulation surfaces), allows the delivery of a proprietary electrical signal. Tubes of electroCore-approved gel are provided with each unit. The subject applies the gel to the stimulation surfaces to maintain an uninterrupted conductive path from the stimulation surfaces to the skin on the neck. The stimulation surfaces are capped when not in use. gammaCore Sapphire produces a low-voltage electric signal consisting of five 5000-Hz pulses that are repeated at a rate of 25 Hz. The waveform of the electric pulses is approximately a sine wave with a peak voltage limited to 24 V when placed on the skin and a maximum output current of 60 mA.(19). Each stimulation is designed to be applied for two minutes (120 seconds), after which the device automatically turns off. Each device allows for multiple stimulations".(19)

6.1.2 DOSING AND ADMINISTRATION

Two-two minute transcutaneous stimulations will be administered every 5 hours (approximately 6:30AM, 11:30 AM, 4:30 PM and 9:30 PM) with no relation to meals. Some patients might miss few stimulations as they might be getting a procedure, have unstable vital signs, or refuse the stimulation, amongst other reasons that might make stimulation not feasible. If vital signs are stable (HR > 60 beats/minute, and SBP> 100 mmHg and MAP> 60 mmhg and saturation > 90% on room, nasal cannula or face mask,), nVNS or Sham will be initiated. We will start by placing gel on the skin of the neck, the device will be placed in direct contact with the gel and the skin. The stimulation will be performed by the patient, with assistance from an IRB approved personnel if the patient is uncomfortable performing it. The stimulation intensity will be increased as directed by the gammaCore pamphlet. Patients will be informed that they may or may not feel a tingling sensation with the investigational device and the sham device. Two 2 minutes stimulation will be provided. Tolerance will be assessed during and directly after stimulation and every 5 hours afterwards as directed by the intensivist on call.

If a digital subtraction angiography is being performed for vasospasm, nVNS will be delivered to assess its effect on cerebral vasospasm.

6.2 PREPARATION/HANDLING/STORAGE/ACCOUNTABILITY

6.2.1 ACQUISITION AND ACCOUNTABILITY

Electrocore is providing gammaCore devices, providing expertise related to study design and execution and will provide device training prior to study initiation. ElectroCore will not be involved in the acquisition of data. Devices will be tracked using a device accountability log.

6.2.2 FORMULATION, APPEARANCE, PACKAGING, AND LABELING

gammaCore (nVNS) Sapphire(19)

The device or its immediate package will bear a label with the following information:

- 1- The name and place of business of the manufacturer, packer, or distributer
- 2- The quantity of contents
- 3- The following statement "CAUTION-Investigational device. Limited by Federal (or United States) law to investigational use"
- 4- The labels will describe all relevant contraindications, hazards, adverse effects, interfering substances or devices, warnings, and precautions

